Anticoagulation treatment reduces the risk of IS by 70% in patients with AF and may potentially prevent premature death and cognitive impairment.⁷ As a large proportion of AF episodes remain asymptomatic¹⁵, timely diagnosis of AF remains a major challenge in clinical practice and oral anticoagulant therapy is often initiated only after a stroke.¹⁶ Early diagnosis and initiation of anticoagulant treatment is key to prevent mutilating stroke sequelae. The diagnosis of AF is made by recording the heart rhythm with an electrocardiogram (ECG). The ECG can be a single recording, intermittent recordings, or continuous recording for hours or days, and several types of devices for ECG monitoring exist. In patients with intermittent (paroxysmal) AF, the diagnosis is often missed by single or repeated ECG recordings, while prolonged continuous ECG-monitoring improves the detection rate.¹⁷ Long-term assessment of the heart rhythm is usually performed by a conventional Holter monitor system which requires a recording device coupled to electrodes on the chest.¹⁸ Although an important diagnostic improvement when implemented in the 1960ies, the Holter monitoring system usually features brief testing intervals (24-72 hours), is susceptible to

disruptions and have high operational expenses. Because of the latter, there is a scarcity of these devices in numerous hospitals, which frequently results in lower utilization rates than recommended, and consequently extensive waiting lists.¹⁹ Other devices for AF-detection include thumb-ECG devices (TED) and implantable loop recorders (ILR). TEDs have been used in previous cohort studies and AF screening studies, but have limited heart rhythm monitoring time and consequently lower sensitivity to intermittent arrhythmias.^{20,21} ILRs have also been used in a previous AF screening study⁵ and allow for continuous rhythm monitoring over years, but require surgical procedures. Watches with heart rate monitoring based on arterial pressure waves cannot be used for clinical diagnostics.⁷ Another alternative is patch ECG-devices, which in smaller studies have been shown to be well suited for AF screening.²²⁻²⁴

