ventricular arrhythmias, SA/AV-block, and other arrhythmias), timing, duration, heart rate of arrhythmias, symptoms and duration of the heart rhythm recording. All study participants will receive information about the test results. A new assessment of HRQoL and medication is planned 6 months post intervention. Initiation and adherence to anticoagulation therapy will be assessed both by questionnaires and by linkage to the Norwegian Prescription Register. Incidence of stroke, cardiovascular and all-cause mortality will be obtained from the Tromsø Study through linkage to national registries.

Safety: In the event of clinically relevant arrhythmias, participants will be contacted as soon as possible. Feedback to the participants will be provided by specially trained physicians and nurses. Participants diagnosed with cardiac arrhythmia or other cardiac abnormal findings will receive advice on follow-up with their general practitioner or be referred to a cardiologist depending of type of arrhythmia. Anticoagulation therapy and other treatments will be recommended if indicated according to current guidelines. The study centre will assist participants who need help to book an appointment for further assessments in cases where this is necessary. An information video about AF will be made in collaboration with the National Association for Heart and Lung Diseases (LHL) to provide general information about AF and potential benefits and risks related to anticoagulant treatment.

Definition of outcomes and other variables of interest: Definition of AF outcome for research question 1 and 2: Paroxysmal AF will be defined as the presence of AF episodes ≥ 30 seconds. In addition, we will register total time in AF (AF burden), beats per minute and concomitant symptoms. Similarly, other tachycardias as atrial flutter (≥ 30 seconds), supraventricular and ventricular tachycardias (cut-offs ≥ 15 seconds and 5 complexes) will also be registered. Initial evaluation will be performed by specially trained research nurses. All positive findings and a similar number of negative tests will be evaluated by a blinded end-point committee of three experts. In case of disagreement the majority will define classification of the outcome.

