Cognitive test performance outcome for research question 3: Scores on the 12-word immediate recall test, the digit symbol coding test and the Mini-Mental State Examination (MMS-E). AF outcomes will be as for question 1 and 2. “Health related quality of life (HRQoL)” outcome for research question 4: A single summary index value (utility score) using a predefined scoring algorithm of the HRQoL EuroQol-5 Dimension (EQ5D) and health anxiety using the Whiteley Index. EQ5D is a standardized instrument developed by the EuroQol group to measure HRQoL and consists of two parts a descriptive system comprising five dimensions (mobility, self-care, usual activities, pain/discomfort and anxiety/depression) and visual analog scale measured ranging from 0 to 100 where patients rate their perceived health status, with 0 being "worst imaginable health state" and 100 being "best imaginable health state." Whiteley Index consists of 14 items, and participants respond on a scale from "not at all" to "very much" or similar gradations.

Relevant echocardiographic variables are atrial size (LAVI, Left Atrial volume Index) and atrial strain (LA reservoir strain). Relevant MRI measures are global and segmental atrophy, volume of white matter lesions, size, presence and number of clinical and subclinical infarcts and micro hemorrhages.

Statistics and analyses: The associations between the primary outcome defined as AF presence(yes/no) and AF burden (number of hours with AF) and prespecified risk factors (traditional CVD risk factors and novel echocardiographic measures) will be examined using multiple regression analyses taking repeated measures within individuals into account by the use of generalized linear mixed effect models and linear mixed effect models, respectively. Linear and logistic (binary or ordinal) regression models with adjustment for relevant confounders will be chosen as appropriate when examining the cross-sectional associations between cognitive test performance and HRQoL outcomes and AF depending on the type of outcome variable (continuous, dichotomous or ordinal). Incidences will be reported as the number of events per 100 years at risk. Censoring for the composite outcome will be done at an event, death of other cause or end of follow-up. Hazard ratios (HRs) will be obtained by Cox regression with adjustment for relevant cofactors. Suitable statistical software will be used for analyses and an experienced statistician will be consulted.

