3.2 PROJECT ORGANISATION AND MANAGEMENT

The role of the PhD candidate: The PhD candidate will be recruited and employed in a 50% position from April 2025. Prior to start all relevant approvals (REC and PVO) will be obtained by the project leader. The PhD candidate will work in close collaboration with the Tromsø Study group, utilizing available infrastructure provided by the Tromsø Study. Tromsø 8 starts in march 2025 with the first visit. 10,000 participants will subsequently be invited to visit 2 starting in April 2025, where NT-proBNP is measured. Based on NT-ProBNP results, participants will be selected and long-term recordings with ECG247 are conducted. The infrastructure at T8 will be essential for conducting blood tests and ECG247 sensor logistics. The management of the ECG247 sensor monitoring is performed by specially trained nurses, but the PhD candidate will be involved in this work to have first line details of the workflow. Postal deliveries of sensors for self-administration will be performed together with the research nurses. General feedback to the Tromsø participants will be standardized and provided electronically. The PhD candidate will under supervision develop an information video in collaboration with LHL. The PhD candidate will organize the data bases and perform data analyses,

drafting and revision of manuscripts according to timeline presented the electronic application form and Gantt chart below. The candidate will be affiliated with the research group Brain and Circulation at UiT and have a shared office space with other PhD students. The candidate will join the national AFIB network (afib.no) and the Norwegian PhD school of heart research (NorHeart (norheart.no)). The four manuscripts of the PhD project will address research questions 1-4 and will be published in international peer-reviewed journals. Furthermore, the PhD student will participate in the PhD program for medicine and health sciences at UiT, which includes completing at least 30 credits of required coursework.

Gantt chart of study timeline	2025				2026				2027				2028				2029				2030				2031					
	1	2	3	4	1	2	3	4	1	2	3	4	1	2	3	4	1	2	3	4	1	2	3	4	1	2	3	4		
Participant recruitment and data collection																														
Mandatory PhD courses																														
Data analysis, drafting, and publication article 1																														
Data analysis, drafting, and publication article 2																														

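### AF burden is fixed as raw hours in AF with no recording-time denominator, so it measures how long the self-applied sensor was worn as well as the disease

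*Protocol*

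**What the plan says.** All of the following is in protocol section 1.3 unless noted.

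- **Burden, outcome definition** (Definition of outcomes): "In addition, we will register total time in AF (AF burden), beats per minute and concomitant symptoms".
- **Burden, analysis definition** (Statistics and analyses): "AF burden (number of hours with AF". The unit is hours, and neither place gives a denominator.
- **Presence** (Definition of outcomes): "Paroxysmal AF will be defined as the presence of AF episodes ≥ 30 seconds".
- **Models** (Statistics and analyses): presence and burden are related to risk factors and echocardiographic measures "by the use of generalized linear mixed effect models and linear mixed effect models, respectively". No recording-time term is named.
- **Recording time** (list of registered variables under Intervention): the list ends with "symptoms and duration of the heart rhythm recording". It is collected but not used again.
- **Delivery** (section 3.2): "Postal deliveries of sensors for self-administration". No target, minimum or common recording length is given.
- **Background** (section 1.1): for intermittent AF, "prolonged continuous ECG-monitoring improves the detection rate".

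**The concern.** Hours in AF equal the fraction of time spent in AF multiplied by the time recorded. Only the first factor describes the participant's disease; the second describes how long a home-applied device stayed on and transmitted. When recording length is left to vary, raw hours rank people partly by adherence.

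Two consequences follow. Variation in wear time unrelated to any risk factor adds noise to burden, and ties the size of every regression coefficient to the average recording length in this study. If wear time is related to a predictor (age, cognition and phone handling are plausible routes), the predictor acquires an association with hours even where true burden is equal. The affected questions are burden in relation to risk factors (Question 1), echocardiographic prediction of burden (Question 2), and Question 3 where burden is reused as the AF measure.

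**Working it through.** **The plan's own figures.** The protocol gives no wear times, AF fractions or episode rates, so there is no figure on this point to reproduce. Its only design calculation is the 80% power for 4.0% against 2.4% with 2000 per group. That is reproduced at about 79.5% with a continuity correction and 82.0% without (two-sided 0.05), and it does not enter this point.

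**Inputs.** From the protocol: burden is total time or hours in AF; presence is any episode of at least 30 seconds; no recording length is stated. Assumed for illustration: wear times of 1, 3, 7 and 14 days, AF fractions of 1%, 5% and 10%, and the episode rates used in step 4.

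**Step 1: raw hours.** Hours in AF = fraction × 24 × days recorded.

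| True AF fraction | 1 day | 3 days | 7 days | 14 days |
|---|---|---|---|---|
| 1% | 0.24 h | 0.72 h | 1.68 h | 3.36 h |
| 5% | 1.2 h | 3.6 h | 8.4 h | 16.8 h |
| 10% | 2.4 h | 7.2 h | 16.8 h | 33.6 h |

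The fraction cancels in the ratio, so 7 against 3 days gives 7/3 = 2.33 in every row. The order of two people can also reverse: a 5% burden recorded for 7 days scores 8.4 h, above a 10% burden recorded for 3 days (7.2 h). Divided by recording time, each row returns its own fraction at every wear time.

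**Step 2: effect on a coefficient without confounding.** Take a true difference of 10% against 5%. With everyone recorded for 3 days it is 7.2 − 3.6 = 3.6 h; with everyone recorded for 7 days it is 16.8 − 8.4 = 8.4 h. The same biological difference gives two estimates, so hours cannot be interpreted without the recording length.

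**Step 3: would a covariate repair it?** Not for burden. Recording time multiplies the fraction, so hours rise with days at a slope of 24 × fraction, which differs between people. An additive wear-time term in the linear model removes only an average slope. The outcome itself has to be rescaled.

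**Step 4: presence, as a secondary matter.** Suppose a person with paroxysmal AF has episodes as a Poisson process at rate r per day. P(at least one seen) = 1 − exp(−r × days).

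- r = 0.1: 0.259 at 3 days, 0.503 at 7 days, ratio 1.94.
- r = 0.05: 0.139 and 0.295, ratio 2.1.
- r = 0.2: 0.451 and 0.753, ratio 1.7.
- r = 0.1, but 6 against 7 days: 0.451 and 0.503, ratio 1.12.
- r = 0.1, 3 against 7 days, with half of AF cases assumed persistent and seen at once: 0.5 + 0.5 × 0.259 = 0.63 and 0.5 + 0.5 × 0.503 = 0.75, ratio 1.19.

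These are detection chances among people who have AF, not population prevalences. From the numbers needed to screen of 45 to 23 in the power paragraph, the protocol expects about 2% to 4% detected. If prevalence is the same in both groups it cancels in the ratios.

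**The case against.** The strongest reply is that the protocol registers recording duration and does not forbid its use, and that a statistical analysis plan not shown here may bring it in. For AF presence this stands. Thirty seconds defines an episode, and a recording-time term in the presence model is ordinary analysis-plan content. For burden it does not stand, because the protocol itself fixes the unit as hours, twice; a later plan would have to override that.

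Three stronger readings are tempting and are not supported.

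- **The AF–cognition association is biased as planned.** The cognition and quality-of-life regressions are to be adjusted for relevant confounders, and recording duration could be one of them. More generally, nothing in the protocol gives the spread of wear times or links them to age, sex or cognition. Without such a link the result is noise and an arbitrary scale.
- **Prevalence ratios will be about 1.9 through wear time alone.** That requires one whole group at 3 days and the other at 7, with all AF intermittent. Milder assumptions give 1.12 to 1.19. Section 1.3 also provides user guides, a help-desk and trained nurses, which may narrow the spread of wear time.
- **Pooling with the national projects will fail.** Section 1.2 says the outcomes are harmonised, the other definitions are not visible, and hours can be converted to a percentage because duration is recorded.

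It is also fair to say that a percentage is not immune. The app gives immediate feedback on rhythm disturbances, so some participants may stop recording after AF is found.

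**Conclusion.** The point holds for AF burden. As defined, it is proportional to recording time, with a ratio of 2.33 for 7 against 3 days at any true burden. That proportionality is arithmetic; how much it matters depends on how widely wear time varies and whether it is related to the risk factors studied. The protocol is silent on both, so noise and a study-specific scale are expected if recording lengths differ, while bias is possible but not shown.

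For AF presence the matter is a recommended precaution and not an error in the definition. The scope is the epidemiological questions. The randomised comparison of ischaemic stroke and cardiovascular death, and its 80% power, do not use burden and are untouched.

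**What to change.** In section 1.3, under both Definition of outcomes and Statistics and analyses:

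1. Define AF burden as time in AF divided by analysable recording time, in percent. Weight by recording time, or add a sensitivity analysis excluding very short recordings. Keep raw hours as descriptive only.
2. For AF presence, account for the registered recording duration in the model, for example as a covariate or as time to first AF censored at the end of analysable recording. A log-time offset with a complementary log-log link is less attractive: it forces the cumulative hazard of detection to be proportional to recording time for everyone, and so can over-correct where AF is persistent.
3. Report age- and sex-specific prevalence also at one common recording length, as a sensitivity analysis.

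The cost is wording and analysis. Duration is already registered and the system stores ECG quality, so no new data are needed. The downside is small: percent burden is imprecise for short recordings, and it can be affected if participants stop after AF feedback.

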The STROKESTOP II study investigates the potential of NT-proBNP as a stratification tool to improve efficacy of AF screening in a randomized population-based study.³⁵ High and low risk groups were defined according to a cutoff of NT-proBNP $\geq 125\text{ng/L}$. New AF was detected in 2.6% of all patients and 4.4% in the high risk group. A recent subgroup analysis from the randomized LOOP study³⁶ suggests that in an older population with additional stroke risk factors, ILR screening is associated with a significant reduction in stroke risk among participants with baseline NT-proBNP above median but not among those having lower levels.³⁶ These results support the potential of NT-proBNP to improve the benefit of AF screening and possibly aid in risk stratification for preventive treatment. However, the utility of NT-proBNP for targeting AF screening and prevention of AF consequences needs to be addressed in well-designed randomized trials.

The risk of IS in patients with AF is presumed to arise from emboli generated by structural and functional alterations within the atria, where a pro-thrombotic milieu is established, particularly in the left atrial appendage.³⁷ Consequently, a new concept of atrial cardiomyopathy has evolved, defined by complex structural, functional and electrophysiological changes, affecting the atria with the potential to produce clinically relevant manifestations.³⁸ Several transthoracic echocardiographic parameters have emerged as promising biomarkers of AF. These include left arterial volume and left arterial function assessed by strain which are associated with AF in patients at risk^{39,40} and in patients with IS of undetermined source.^{41,42} However, knowledge of association between echocardiographic parameters and paroxysmal AF in a general population is limited.

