1.3. RESEARCH QUESTIONS AND HYPOTHESES, THEORETICAL APPROACH AND METHODOLOGY

The significance and originality of the proposal:

We propose to perform a randomized controlled screening trial within the Tromsø 8 population-based cohort study, applying monitoring of heart rhythm with leading sensor technology (ECG247) in participants with elevated levels of NT-proBNP. We will add important data to ongoing screening trials by including comprehensive clinical assessments of included subjects. The overall aim of the project is to assess the primary hypothesis that continuous ECG-monitoring in individuals with elevated NT-pro-BNP and subsequent anticoagulant treatment according to current international guidelines leads to reduced incidence of the composite outcome ischemic stroke and cardiovascular death.

The work performed by the PhD student for which we seek funding by this application will create new knowledge related to:

- 1) the age and sex specific prevalence of various burdens of AF (duration, frequency, heart rate and symptoms) and association with repeated measured risk factors in the Tromsø Study
- 2) the association between AF and echocardiographic parameters
- 3) the association between AF, findings on brain MRI and results of cognitive tests
- 4) participants perception of health-related quality of life before and after AF detection by continuous ECG monitoring

The specific research questions which will be addressed in the present PhD project are:

Question 1: What is the age and sex specific prevalence of paroxysmal AF (considering duration, frequency, heart rate and symptoms) and its association with repeated measured cardiovascular risk factors among Tromsø Study participants with elevated levels of NT-Pro-BNP?

Question 2: Can the presence and burden of AF (duration, frequency, heart rate) in the general population with elevated level of NT-ProBNP be predicted by comprehensive echocardiographic evaluation?

Question 3: Is atrial fibrillation associated with cognitive test performance in subjects with elevated NT-proBNP and is this association modified by specific MRI findings?

Question 4: Does detection of AF by continuous ECG monitoring influence health related quality of life?

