Power estimates: Power estimates are customized to test the primary hypothesis that continuous ECG-monitoring in individuals with elevated NT-proBNP and subsequent anticoagulant treatment according to current international guidelines leads to reduced incidence of the composite outcome IS and cardiovascular death. According to a previous study performed at Sørlandet⁵⁰ with ECG247 the number needed to screen was 45 to detect one unrecognized case of AF in subjects at risk for stroke. When restricting screening to the population with NT-proBNP level > median the number needed to screen may be reduced to 31³⁶ and even 23³⁵ in an older population. The 6-year risk of the composite outcome is expected to be 4% in the control group. Risk in the group screened where no AF is found varies from 2 to 3%. In the group screened where AF is found the risk is 10% (30% risk of IS during a 6-year period, reduced by 70% with oral anticoagulant therapy). If the 6-year risk among screened participants without AF is 2.2%, and we include 2000 participants in each group, there is 80% power to detect a significant difference ($\alpha=0.05$) between control and intervention groups with estimated risk of 4.0% vs. 2.4% for the composite outcome, respectively. Based on the results of the Loop and StrokeStop study and the younger population in the Tromsø study, we expect to reduce risk of the composite outcome from 4% in the control group to 2.4% in the screening group. Compared to previous epidemiological studies, the planned epidemiological projects for the PhD student will have sufficient statistical power to explore meaningful associations.

Data handling and storage: EUTRO is a research administrative tool that will be used for data collection and storage in Tromsø 8. EUTRO provides a complete overview of a study's total research material, including responses to questionnaires, biological material, health data, and project information. EUTRO is integrated within TSD (services for sensitive data located at University of Oslo) which assures and facilitates anonymized data handling and storage according to present regulations and research needs. All data security is taken care of according to the requirements from the Norwegian Data Protection Authority, and privacy is well maintained in the system. The system ensures compliance with the Health Research Act and GDPR requirements for security, handling, and administration of sensitive research data and biological material.

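### Hours in AF are assigned a linear mixed model although about 96-98% of the values will be zero; the burden analyses of Questions 1 and 2 need a two-part model

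*Protocol*

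**What the plan says.** All places are in protocol section 1.3 unless stated.

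- Statistics and analyses: the association analyses have a "primary outcome defined as AF presence(yes/no) and AF burden (number of hours with AF". Both parts are to be related to risk factors and echocardiographic measures "by the use of generalized linear mixed effect models and linear mixed effect models, respectively". The last word pairs AF presence with the generalized model and hours with the linear one.
- Definition of outcomes: AF means episodes of at least 30 seconds, and burden is the total time: "In addition, we will register total time in AF (AF burden), beats per minute and concomitant symptoms". A monitored person with no AF therefore has a burden of 0 hours.
- Research questions: Question 2 begins "Can the presence and burden of AF (duration, frequency, heart rate", so duration is part of what is asked. Question 1 also names duration.
- Power estimates: in an earlier study with the same sensor, "the number needed to screen was 45 to detect one unrecognized case of AF in subjects at risk for stroke". With restriction to raised NT-proBNP, "the number needed to screen may be reduced to 31³⁶ and even 23³⁵ in an older population" (the superscripts are citation numbers).
- Exclusion criteria: self-reported AF is excluded, so non-zero hours come essentially from newly found AF.

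For burden, the text gives no transformation, no two-part model, no robust or bootstrap interval, and no restriction to people with AF.

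**The concern.** A linear model with one residual variance describes a roughly symmetric response with constant spread. Hours in AF would be a large spike at zero plus a few values running from 30 seconds up to the whole recording. Two things follow. The slope cannot tell a reader whether a factor goes with having AF or with having it for longer, although Questions 1 and 2 ask about both. And the standard error rests on a constant variance that fails as soon as a factor is related to AF. At stake is the interpretation and precision of the burden results in the two papers planned for those questions.

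**Working it through.** **Inputs from the protocol.** Monitored participants: 2000 (Power estimates). Number needed to screen (NNS): 45, 31 or 23 (same place). As a consistency check, section 1.1 reports "New AF was detected in 2.6% of all patients and 4.4% in the high risk group", and 1/0.044 = 22.7, which agrees with 23. The protocol states no zero share and no power for the hours model, so there is no figure of its own to reproduce here. Its 80% power concerns the composite outcome.

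**Step 1: share of zeros.** Expected AF cases = 2000/NNS; share of zeros = 1 - 1/NNS.

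| NNS | AF cases | Zeros |
|---|---|---|
| 45 | 2000/45 = 44 | 97.8% |
| 31 | 2000/31 = 65 | 96.8% |
| 23 | 2000/23 = 87 | 95.7% |

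**Step 2: what the slope estimates.** Let p(x) be the probability of AF and H the hours in someone with AF. Then E[hours | x] = p(x) × E[H | x]. A single slope reflects the change in this product, so its two components cannot be separated.

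**Step 3: why the interval fails only when there is an effect.** If H does not depend on x, Var(hours | x) = p(x)E[H²] - p(x)²E[H]². For small p this is close to p(x)E[H²], so the variance rises with the risk of AF. At an odds ratio of 2.0 per SD, the odds at +2 SD are 2² = 4 times those at the mean, and the variance is nearly that much larger at the points with most leverage on the slope. With no effect, p(x) is flat and the constant-variance interval is sound.

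**Step 4: size, by simulation.** There were 1000 runs per setting with n = 2000 and one burden value per person, so the mixed model reduces to ordinary linear regression. AF occurrence follows a logistic model in one factor. Assumptions not in the protocol: the form of the factor, its odds ratio, and hours among AF cases (lognormal, median 3 h, log-SD 1.0 or 1.8, capped at 168 h). Ranges run over the three yields and both spreads. Monte Carlo error near 95% is √(0.95 × 0.05/1000) = 0.7 percentage points.

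Coverage of the nominal 95% interval for the linear slope on hours:

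| Factor | OR 1.5 | OR 2.0 |
|---|---|---|
| Normal (OR per SD) | 91-93% | 85-90% |
| Skewed (OR per SD) | 75-81% | 56-69% |
| Binary, 30% prevalence | 93-95% | 88-93% |

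With no effect, coverage is 94.5-97.6% across all three forms.

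**Step 5: sensitivity to the assumptions.** With log-uniform hours from 30 s to 168 h and a normal factor, coverage is 92-93% at OR 1.5 and 88-89% at OR 2.0. Further runs gave 90-93% and 87-90%, and 78-88% when the factor also affects duration. Ten participants hold about 65-89% of all AF hours in these runs.

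**The case against.** Three arguments on the other side deserve weight.

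*The binary model is already planned.* A reader might infer that real predictors of AF would mostly be missed. The documents do not support that: the same sentence gives AF presence its own binary model. In the step 4 simulation (normal factor, OR 1.5 per SD) that model has 76-96% power, against 24-65% for the linear model on hours. The gap is not a gain from changing the burden model, because the higher figure belongs to an analysis already in the protocol. With log-uniform hours independent of the factor, the planned logistic model had 74% power at 1/45 and 94% at 1/23. A two-degree-of-freedom joint test had 65% and 91%, and the duration part alone rejected in 5-7% of runs, about its false-positive rate. When the factor also affects duration, the linear model's power is close to that of the joint test. This argument stands in full, so the case for change does not rest on power.

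*Intervals are not too narrow in general.* This stands too. With no effect coverage is about nominal, so false positives are not materially inflated, and for a weak binary factor the shortfall is slight.

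*Details may sit in an SAP, and a statistician is to be consulted.* This stands in part. The protocol does not fix the analysis set or scale for burden, so the linear model could be meant for AF cases only. Including everyone monitored is the more natural reading, however. On the other reading, raw and highly skewed hours in 44 to 87 people would still be modelled as Gaussian. The model family is also a stated choice, not a gap.

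One further inference fails. The statistics text calls presence and burden the primary outcome, but of the association analyses. The trial's primary hypothesis, power estimate and Cox analysis concern ischemic stroke and cardiovascular death, and nothing here touches them.

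**Conclusion.** The concern holds, limited to the burden analyses of Questions 1 and 2. The zero share of about 96-98% follows directly from the protocol's own yields, and a constant-variance linear model does not fit such a response, whatever the hours among AF cases look like. The slope confuses occurrence with duration, and its intervals under-cover for factors with a real effect: about 90-93% at OR 1.5 per SD and 85-90% at OR 2.0 for a normal factor, and lower if the factor is skewed or also affects duration. These coverage figures depend on an assumed recording length and distribution of hours, which the protocol does not give. They show the direction and plausible size, not exact values. Severity is moderate: the tests for predictors of AF occurrence and the randomised comparison are sound in this respect, and the model can be corrected before any burden data are analysed.

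**What to change.** In Statistics and analyses, replace the linear model for burden with a two-part analysis:

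1. Keep the planned logistic model for any AF among all monitored participants.
2. Among AF-positive participants only, regress log burden, or ordinal burden classes, on the same factors.

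Report the two parts separately. Label the second exploratory, because it rests on about 44 to 87 people. Robust standard errors on the existing linear model would not be enough: in the step 4 simulation they still covered only about 77-90% for a skewed factor, and the slope would still mix the two questions.

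The cost is about one sentence of protocol text and no extra data. The downsides are two coefficients per factor instead of one, and low precision in the second part. The change should be made before burden data are seen, so that the model is not chosen after the results.
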